## 5.5. Withdrawal/Stopping Criteria

A subject may withdraw from study treatment at any time at his/her own request, or may be withdrawn at any time at the discretion of the investigator for safety, behavioural, or administrative reasons. If a subject withdraws from the study, he/she may request destruction of any samples taken, and the investigator must document this in the site study records. As the aim of this study is to evaluate the use of the mepolizumab liquid drug product, in autoinjector presentation, for delivery of mepolizumab, subjects who permanently withdraw from study treatment will also be withdrawn from the study (see Section 5.5.1). Reasons for premature discontinuation of study treatment will be captured in the CRF.

## 5.5.1. Withdrawal from the Study

Subjects who have withdrawn from the study should complete assessments for the Early Withdrawal Visit, 4 weeks after the last dose of mepolizumab (see Time and Events Table, Section 7.1).

A reason for the withdrawal from the study must be captured in the eCRF.

A subject must be discontinued if any of the following criteria are met:

- Withdrawal of consent
- Lost to follow-up

A subject will also be withdrawn from the study, in consultation with the medical monitor and principal investigator, if any of the following stopping criteria are met:

- Laboratory parameters: Clinically important changes in laboratory parameters identified
- ECG: Clinically significant abnormality identified during the study that meet the QTc stopping criteria described in Section 5.5.3
- Liver Chemistry: Meets any of the Liver chemistry stopping criteria (see Section 5.5.2 and Appendix 4
- Pregnancy: Positive pregnancy test (see Appendix 3). Pregnancy and pregnancy outcomes of subjects exposed to mepolizumab will be followed

The following actions must be taken in relation to a subject who fails to attend the clinic for a required study visit:

- The site must attempt to contact the subject and re-schedule the missed visit as soon as possible.
- The site must counsel the subject on the importance of maintaining the assigned visit schedule and ascertain whether or not the subject wishes to and/or should continue in the study.

- In cases where the subject is deemed 'lost to follow up', the investigator or designee must make every effort to regain contact with the subject (where possible, 3 telephone calls and if necessary a certified letter to the subject's last known mailing address or local equivalent methods). These contact attempts should be documented in the subject's medical record.
- Should the subject continue to be unreachable, only then will he/she be considered to have withdrawn from the study with a primary reason of "Lost to Follow-up".

## 5.5.2. Liver Chemistry Stopping Criteria

**Liver chemistry stopping and increased monitoring criteria** have been designed to assure subject safety and evaluate liver event etiology (in alignment with the Food and Drug Administration [FDA] premarketing clinical liver safety guidance). http://www.fda.gov/downloads/Drugs/GuidanceComplianceRegulatoryInformation/Guid ances/UCM174090.pdf

### Liver Chemistry Stopping and Increased Monitoring Algorithm

\*INR value not applicable to subjects on anticoagulants

## Liver Chemistry Increased Monitoring Algorithm with Continued Therapy for ALT ≥3xULN but <8xULN

\*INR value not applicable to subjects on anticoagulants

Required actions and follow-up assessment for all subjects who meet liver chemistry stopping or monitoring criteria are defined in Appendix 4.

### 5.5.2.1. Study Treatment Restart or Rechallenge

Study treatment restart or rechallenge after liver chemistry stopping criteria are met, by any subject participating in this study, is not allowed.

## 5.5.3. QTc Stopping Criteria

- The *same* QT correction formula *must* be used for *each individual subject* to determine eligibility for and discontinuation from the study. This formula may not be changed or substituted once the subject has been enrolled. For example, if a subject is eligible for the protocol based on on QT interval corrected for heart rate by Bazett's formula (QTcB), then QTcB must be used for discontinuation of this individual subject as well.
  - Once the QT correction formula has been chosen for a subject's eligibility, the *same formula* must continue to be used for that subject *for all QTc data being collected for data analysis*. Safety ECGs and other non-protocol specified ECGs are an exception.
  - The QTc should be based on single or averaged QTc values of triplicate electrocardiograms obtained over a brief (e.g., 5-10 minute) recording period. For example if a routine ECG demonstrates a prolonged QT, obtain 2 more

ECGs over a brief period and then use the averaged QTc values of the 3 ECGs to determine whether patient should be withdrawn from the study.

A subject who meets either of the bulleted criteria below will be withdrawn from the study:

- QTc >500 msec OR Uncorrected QT >600 msec
- Change from baseline (Visit 2) of QTc >60 msec

For patients with underlying **bundle branch block**, follow the discontinuation criteria listed below:

Baseline (Visit 2) QTc with Bundle Branch Block	Discontinuation QTc with Bundle Branch Block
<450 msec	>500 msec
450 – 480 msec	≥530 msec

## 5.6. Subject and Study Completion

A completed subject is one who has completed the End of Study (Week 12) visit.

The end of the study is defined as the last subject's last visit.

## 6. STUDY TREATMENT

## 6.1. Investigational Product and Other Study Treatment

The term 'study treatment' is used throughout the protocol to describe the mepolizumab drug product in autoinjector received by the subject as per the protocol design.

Mepolizumab liquid drug product will be supplied by GSK in Type I glass syringes with staked needles (1/2 inch x 29 gauge thin wall), sealed with latex-free rubber plungers. These will be assembled in single use, disposable autoinjectors to enable automatic delivery of the drug product. Each device will deliver 100mg mepolizumab in 1.0mL. The formulation contains sodium phosphate, citric acid, sucrose, EDTA and polysorbate 80.

	Study Treatment
Product name:	Mepolizumab (NUCALA) (SB240563)
Device:	Prefilled syringe contained within an autoinjector
Formulation description:	100 mg/mL mepolizumab with sodium phosphate, citric acid,
	sucrose EDTA and polysorbate 80
Dosage form:	Sterile, liquid formulation
Unit dose	100 mg/mL; 1.0mL (deliverable)
strength(s)/Dosage level(s):	
Route of Administration	SC injection
Dosing instructions:	SC dose in thigh, abdomen or upper arm every 4 weeks
Physical description:	Clear to opalescent, colourless to pale yellow sterile solution for
mepolizumab	SC injection in a single-use, prefilled syringe contained within an
	autoinjector
Physical description of	Single use, disposable autoinjector assembled with the prefilled
injection device:	syringe containing the drug product. The autoinjector enables
	automatic delivery of the drug product under the power of a
	spring mechanism following activation of the device. Start and
	end of injection clicks inform the user of correct use. A plastic
	needle cover shields the needle before and after injection to
	minimise the potential for needle stick injuries.
Manufacturer/source of	Prefilled syringe: Prefilled syringe components are procured
procurement:	from Becton Dickinson. Prefilled syringe is filled with drug
	product and assembled at GSK, Barnard Castle, UK.
	Autoinjector: The autoinjector components are manufactured by
	Ypsomed AG and assembled with the prefilled svringe at GSK
	Barnard Castle, UK.

## 6.2. Medical Devices

The GSK manufactured medical devices (or devices manufactured for GSK by a third party) provided for use in this study are injection devices: a prefilled syringe contained within an autoinjector. The devices used in the study are representative of the devices and regionally appropriate device product labeling planned to be marketed for the product.

The components that comprise the prefilled syringe, including glass barrel with prestaked needle and plunger are sourced from Becton Dickinson. The prefilled syringe is filled and assembled at GSK, Barnard Castle.

The autoinjector components are manufactured by Ypsomed AG. The autoinjector components are assembled with the prefilled syringe at GSK, Barnard Castle.

The IFU of these injection devices are provided in the SRM. The instructions were developed and optimised as a result of formative human factors studies and are representative of those that are planned for the product.
GSK medical device incidents, including those resulting from malfunctions of the device, must be detected, documented, and reported by the investigator throughout the study – see Section 7.7.3.

## 6.3. Treatment Assignment

All subjects will be assigned to the same treatment at Visit 2 (Week 0).

## 6.4. Blinding

This will be an open-label, single arm study.

# 6.5. Packaging and Labelling

The contents of the label will be in accordance with all applicable regulatory requirements. The autoinjector will either be labelled with a pictogram plus standard labelling elements or standard labelling without the pictogram.

# 6.6. Preparation/Handling/Storage/Accountability

No special preparation of study treatment is required.

Study treatment must be dispensed or administered according to procedures described herein. Only subjects enrolled in the study may receive study treatment. Only authorised site staff may supply study treatment. All study treatment must be stored in a secure area with access limited to the investigator and authorised site staff.

Mepolizumab will be supplied in a single use prefilled syringe contained within an autoinjector and should be stored in a refrigerator at 2 to 8°C with protection from light. Each injection device will contain 100 mg mepolizumab as a single 1.0 mL injection of the liquid drug product (100 mg/mL). Maintenance of a temperature log at the clinical dispensing sites (manual or automated) is required.

- The investigator or designee must confirm appropriate temperature conditions have been maintained during transit for all study treatment received and any discrepancies are reported and resolved before use of the study treatment.
- Only the subject or previously identified caregiver may administer the study treatment. Whilst on site, all study treatments must be stored in a secure environmentally controlled and monitored (manual or automated) area in accordance with the labelled storage conditions with access limited to the investigator and authorised site staff.
- The investigator, institution, or the head of the medical institution (where applicable) is responsible for study treatment accountability, reconciliation, and record maintenance (i.e. receipt, reconciliation and final disposition records).
- Further guidance and information for final disposition of unused study treatment are provided in the SRM.

- Under normal conditions of handling and administration, study treatment is not expected to pose significant safety risks to site staff.
- A Material Safety Data Sheet (MSDS)/equivalent document describing occupational hazards and recommended handling precautions either will be provided to the investigator, where this is required by local laws, or is available upon request from GSK.
- Subjects will be provided an autoinjector for home use at Visit 3 and asked to follow the information on the IFU with regards to the storage and use of the device. Cool bags and cold packs will be provided to transport the autoinjector from site to home. Subjects will be asked to return the used autoinjector at Visit 4. A record of the dispensing of the autoinjector given to the subject at Visit 3 and collection of the autoinjector returned at Visit 4 will be maintained by the Investigator or designee. The Investigator or designee will also inspect the returned autoinjector to determine if the dose has been dispensed correctly.

# 6.7. Training Session

Training of study treatment, handling and administration techniques by qualified study site personnel will be provided to the study participants at Visit 2, prior to self-administration. The training is designed to be representative of the instruction and training materials that will be used in the post-marketing setting. The training will consist of a walk-through of the IFU for the injection devices by the site personnel. The first injection will then be observed by site personnel and may include feedback to the subject as needed.

# 6.8. Compliance with Study Treatment Administration

A record of the number of autoinjectors dispensed and returned by each subject must be maintained and reconciled with study treatment and compliance records.

## 6.8.1. Self-Administration at the Clinic

Following the training (see Section 6.7) at Visit 2 (Week 0), the subject (and/or caregiver, if applicable) will self-administer the first dose of study treatment by SC injection under medical supervision of the investigator or designee at the study site. The subject/caregiver will also administer the dose of study treatment at the clinic under medical supervision, but without further training, at Visit 4 (Week 8). Observations about the injection will be recorded by the investigator or designee using a checklist for the doses administered in the clinic. Details of the Observer Checklist can be found in the SRM. The subject will complete a patient diary with a visual analogue scale (VAS) indicating the pain experience immediately following, 1- and 24-hours after the dose.

The date, time of the dose, person administering the dose (subject/caregiver) and site of administration (thigh, abdomen or upper arm [caregiver only]) of each dose administered in the clinic will be recorded on the observer checklist and in the source documents.

Subjects will be monitored for 1 hour after mepolizumab self-administrations in the clinic at Visit 2 and Visit 4. In the event of an acute severe reaction (e.g., anaphylaxis)

following administration of study treatment, there are personnel/staff onsite at the treatment facility who are appropriately trained in basic life support to manage the subject including administration of medications (e.g., epinephrine), and have access to a system that can promptly transport the patient to another facility for additional care if appropriate.

## 6.8.2. Self-Administration Outside the Clinic

The subject (or caregiver) will self-administer the dose of study treatment outside the clinic and without observation during Week 4, up to 24 hours after attending clinic Visit 3. The subject/caregiver will complete a checklist of the steps required to use the autoinjector, which will also include the date and time of dose, site of injection, person administering the dose (subject/caregiver) and the ease with which the subject/caregiver was able to complete each of the critical steps required to administer the dose from the autoinjector. In addition, the subject will complete the patient diary capturing the pain experienced by the subject immediately following, 1- and 24-hours after the dose.

Subjects will be instructed to contact clinical study staff if they have concerns or questions regarding self-administration. They will have the option of returning to the clinical site for further training or assistance with self-administration. Requirement for additional training will be documented.

Compliance with the autoinjector will be assessed through reviewing the subject completed checklist, inspection of the returned autoinjector and querying the subject during the next site visit (Visit 4) and documented in the source documents.

For self-administration of mepolizumab outside of the clinic (at home), subjects should be instructed to call the investigator and/or go to an Emergency Department for any unusual symptoms (e.g. skin rash [hives] or redness, swelling of the face or mouth, becoming wheezy, coughing or having difficulty in breathing and/or feeling weak or light headed).

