## 3. OBJECTIVE(S) AND ENDPOINT(S)

The aim of this study is to assess the correct real-world use of the mepolizumab liquid drug product in autoinjector for the repeat self-administration of mepolizumab subcutaneously by determining the proportion of subjects with severe eosinophilic asthma who are successfully able to self-administer a dose of mepolizumab. For the purposes of this study, 'self-administration' is defined as either the administration of mepolizumab liquid drug product in autoinjector by the subject themselves or by their caregiver.

The objectives and endpoints associated with these objectives are outlined below:

Objectives	Endpoints
Primary	
• To assess the use of the combination product, mepolizumab liquid drug product in autoinjector for the subcutaneous self-administration of mepolizumab by subjects with severe eosinophilic asthma	• Proportion of subjects successfully able to self-administer their observed third dose at Week 8
Secondary	
• To assess the use of mepolizumab liquid drug product in autoinjector outside the clinic setting	• Proportion of subjects successfully able to self-administer their unobserved second dose outside the clinic setting at Week 4

	Objectives		Endpoints
Ot	ner		
•	To assess the use of mepolizumab liquid drug product in autoinjector both inside and outside of the clinic setting	•	Proportion of subjects successfully able to self-administer their observed first dose at Week 0
		•	Proportion of subjects successfully able to self-administer both their unobserved second dose and observed third dose at Weeks 4 and 8
		•	Proportion of subjects successfully able to self-administer all three doses at Weeks 0, 4 and 8
•	To evaluate autoinjector use & functionality	•	Device usability/functionality questionnaire completed at the End of Study/Early Withdrawal Visit
•	To evaluate any autoinjector injection errors/failures related to use or device performance	•	Evaluation of user/device errors Root cause analysis of each unsuccessful injection
•	To characterise the subject experience of using the mepolizumab liquid drug product in autoinjector	•	Subject Exit Interviews completed over the telephone after the End of Study/Early Withdrawal Visit
•	To assess mepolizumab plasma trough concentrations following the SC administration of mepolizumab liquid drug product in autoinjector	•	Mepolizumab plasma trough concentrations (Ctrough) at Weeks 4, 8 and 12

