- Direct observation of the self-administration using the Observer Checklist if the mepolizumab dose was administered in the clinic, and inspection of the autoinjector
- Subject/caregiver completed checklist and inspection of the returned autoinjector if the mepolizumab dose was administered outside the clinic

A self-administered injection is considered successful if the following criteria are met:

- Use of a correct injection site (abdomen/thigh or upper arm [caregiver only])
- Full dose administration: subject pushes the autoinjector all the way down and holds until either the second click, or the plunger stops moving and the inspection window is filled with the yellow indicator or pushes the autoinjector all the way down and holds for a total of 15 seconds
- No observations are made with respect to the autoinjector, following inspection, which indicates the full dose has not been dispensed

If the above criteria are met, the investigator or designee will confirm the injection was successfully delivered.

Any unsuccessful injection will undergo a root-cause investigation, following a scripted approach, and evaluation to assess whether the unsuccessful injection was associated with the instructions / use of the device or whether it was associated with a device failure using the Autoinjector (Pen) Error/Failure Reporting Form, further details of which can be found in the SRM. All devices will be evaluated by Device Engineering at GlaxoSmithKline (GSK), post-use, to assess overall performance and robustness of the device.

At the End of Study Visit, subjects will be asked to record their overall experience with the autoinjector including device performance.

In all subjects, blood samples for both PK, haematology assessment (which will include blood eosinophil count for the pharmacodynamic effect assessment) and clinical chemistry assessment will be collected at the time points indicated in the Time and Events Table (Section 7.1).

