# 7.3. Assessment of Autoinjector Use

At Visit 2 (Week 0), and at Visit 4 (Week 8), the investigator or designee will observe, using a checklist based on the autoinjector IFU, the ability of the subject/caregiver to (self)-administer the injection. The Observer Checklist (see SRM) will be used to determine if each step, according to the IFU, was completed easily, with some difficulty or not completed/intervention required. Failure to perform one of the critical steps, i.e., correct choice of injection site and a full dose administered (determined by the subject pushing the autoinjector all the way down and holding until either the second click, or the plunger stops moving and the inspection window is filled with the yellow indicator or by the autoinjector being pushed all the way down and held for a total of 15 seconds) will be deemed to be a failure to successfully administer the injectior. In addition, the investigator or designee will be asked to inspect the autoinjector, following each injection, to confirm that the yellow indicator fills the inspection window and the needle guard has locked into place (checked by pressing the needle guard against a firm surface),

as well as noting any additional observations which indicate the full dose has not been dispensed.

Any user errors or device malfunctions will be recorded and reported using the Autoinjector (Pen) Error/Failure Reporting Form (see SRM). Malfunction or failure of the autoinjector meeting the definition of a Medical Device Incident (see Appendix 5), will also require a Medical Device Incident form to be completed and must be reported as described in Section 7.7.3.

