### 2.3. Study Design

Overview of Study Design and Key Features	

The diagram illustrates the study timeline. It begins with Pre-screening (0 to 2 weeks) and Screening (1 to 4 weeks). Key visits are marked: Visit 0 (Pre-screen), Visit 1 (Screen), and Visit 2 (Start of Study). Mepolizumab administration is shown as a series of doses: the first dose is administered in-clinic at Visit 2 (Week 0), the second dose is self-administered out-of-clinic at Visit 3 (Week 4), and the third dose is administered in-clinic at Visit 4 (Week 8). The study concludes at the End of Study (Week 12). A legend indicates that blue triangles represent 'In Clinic' and yellow triangles represent 'Out of Clinic'.
	

Design Features
	
 
• 12-week treatment period, open-label, single arm, repeat-dose, multi-centre study in subjects with severe eosinophilic asthma.
 
• Subjects (or their caregiver, if applicable) will be trained to administer mepolizumab liquid drug product in autoinjector prior to the first dose (Visit 2).
 
• Each autoinjector will have labelling that includes a pictogram plus standard labelling elements, or a standard labelling without the pictogram dependant on the country in which it is being used.
 
• Mepolizumab will be self-administered (by subject or caregiver, if appropriate) under observation in the clinic for first dose (Visit 2) and third dose (Visit 4). The second dose of mepolizumab will be self-administered (by subject or caregiver, if appropriate) at home without observation following Visit 3.
 
• All injections will be assessed by the investigator for success based on             
 
○ Direct observation of the self-administration if the dose was administered in the clinic, and inspection of the autoinjector.
 
○ Subject/caregiver completed checklist if the dose was administered outside the clinic, and inspection of the returned autoinjector.
 
 
 

Main Subject Entry Criteria
	
 
• Subjects aged 12 or older with physician diagnosis of asthma for <math>\geq 2</math> years.
 
 
Either
 
 
• Subjects receiving 100mg subcutaneous (SC) mepolizumab for the treatment of severe eosinophilic asthma every 4 weeks for at least 12 weeks prior to the study.
 

Overview of Study Design and Key Features	

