### 7.2. Secondary Analyses

The following endpoints will be summarised in the same way as the primary endpoint (Section [7.1](#)).

- The number and percentage of subjects successfully able to self-administer their unobserved second dose at Week 4. The denominator for the percentage calculation will be the number of subjects attempting an injection at Week 4.
- The number and percentage of subjects successfully able to self-administer their observed first dose at Week 0. The denominator for the percentage calculation will be the number of subjects attempting an injection at Week 0.
- The number and percentage of subjects successfully able to self-administer both their unobserved second dose at Week 4 and their observed third dose at Week 8. The denominator for the percentage calculation will be the number of subjects attempting an injection at both Week 4 and Week 8.
- The number and percentage of subjects successfully able to self-administer all three doses at Week 0, 4 and 8. The denominator for the percentage calculation will be the number of subjects attempting all three doses at Week 0, 4 and 8.

Data collected on the observer checklist for in-clinic injections and subject completed checklists for home injections will be summarised. The investigator assessment of user/device errors will be summarised by visit. Device usability/functionality assessed by the subject at the end of the study will also be summarised.

Full details of data displays being presented in [Appendix 8: List of Data Displays](#).

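### Can a Week 4 dose given at the clinic under observation be counted as a success for the unobserved, out-of-clinic endpoint?

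*Protocol*

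**What the plan says.** Protocol section 3 and SAP 2.2 define the secondary endpoint as "Proportion of subjects successfully able to self-administer their unobserved second dose outside the clinic setting at Week 4". SAP 7.2 turns this into a count: "The number and percentage of subjects successfully able to self-administer their unobserved second dose at Week 4". It adds: "The denominator for the percentage calculation will be the number of subjects attempting an injection at Week 4". Multiple attempts are handled as in SAP 7.1, so the first attempt is the one analysed.

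Protocol 6.8.2 places this dose away from the clinic with nobody observing, up to 24 hours after Visit 3. It then gives subjects who have concerns a way back to the site: "They will have the option of returning to the clinical site for further training or assistance with self-administration". Footnote e of the Time and Events Table repeats the option and asks that any such need be documented.

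The method of assessment depends on where the dose was given. Protocol 4.1 uses "Direct observation of the self-administration using the Observer Checklist if the mepolizumab dose was administered in the clinic", together with inspection of the device. SAP 2.3 agrees: "Direct observation of the self-administration if the dose was administered in the clinic, and inspection of the autoinjector". Home doses are assessed from the subject or caregiver checklist and the returned device. The list that begins "A self-administered injection is considered successful if the following criteria are met" covers injection site, full dose and device inspection; it does not mention place or observation.

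**The concern.** The endpoint is about unsupervised use, yet the rules that score an injection do not ask whether anyone was watching. A subject who lacks confidence can go back to the site for help with the dose. If the injection is then given there, it can be assessed by direct observation and meet all three success criteria. The table shell for injection success (TAB_INJ1, SAP 14.9) has a single Week 4 row with no split by place. The rule for unscheduled visits (SAP 14.3.2) moves data to the nearest nominal visit at which they were due, and the Week 4 success assessment is itself scheduled at Visit 4, so where such a record would land is not obvious.

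Week 4 is the only single-dose measure of use outside the clinic, and it feeds the Weeks 4 and 8 row and the all-three-doses row. Counting supervised injections as unsupervised successes could only push these percentages up. The subjects concerned are plausibly those least able to manage alone.

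**Working it through.** **Reading the rules together**

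1. *Numerator.* The endpoint carries two conditions, unobserved and outside the clinic. SAP 7.2 drops the second but keeps the first. A dose watched by site staff fails the condition that remains, so it is not a Week 4 success.
2. *Denominator.* SAP 7.2 takes everyone attempting an injection at Week 4, with no condition on place. An observed first attempt at the site belongs in it.
3. *Result.* Steps 1 and 2 put the dose in the denominator and outside the numerator. A new sentence counting such doses as not successful would give the same outcome.
4. *Combined rows.* The Weeks 4 and 8 numerator repeats the unobserved condition. The all-three-doses numerator does not, but its Week 4 component is the same second dose and is naturally read the same way.
5. *Staff help.* If a clinic dose is judged with the Observer Checklist, each step is graded "completed easily, with some difficulty or not completed/intervention required", and Protocol 7.3 makes failure on a critical step a failed injection. On that premise, staff intervention on a critical step already fails. What remains is an on-site, observed, unaided first attempt.
6. *Failed home attempts.* These are already failures under the first-attempt rule. A later retry at the site can enter only the supportive best-attempt summary.

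**Size if the numerator wording were ignored**

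Inputs: group sizes 100 and 50 (Protocol 9.2.2) and exact 95% intervals (SAP 7.1). For x successes in n, the lower limit is the 2.5% quantile of Beta(x, n−x+1) and the upper limit is the 97.5% quantile of Beta(x+1, n−x).

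The plan's own table comes first. For 96%, Protocol 9.2.2 gives 90, 99 (N=100) and 86, 100 (N=50). The formula gives 90.07, 98.90 and 86.29, 99.51. All 22 intervals in that table reproduce after rounding.

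Now suppose k of the tabulated successes were observed at the site. The documents give no value for k; 1 and 3 per label group are assumptions.

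| | Counted as success | Not successful, kept in denominator | Left out |
|---|---|---|---|
| N=100, k=1 | 96/100 = 96% (90.1–98.9) | 95/100 = 95% (88.7–98.4) | 95/99 = 95.96% (90.0–98.9) |
| N=100, k=3 | 96/100 = 96% (90.1–98.9) | 93/100 = 93% (86.1–97.1) | 93/97 = 95.88% (89.8–98.9) |
| N=50, k=1 | 48/50 = 96% (86.3–99.5) | 47/50 = 94% (83.5–98.7) | 47/49 = 95.92% (86.0–99.5) |
| N=50, k=3 | 48/50 = 96% (86.3–99.5) | 45/50 = 90% (78.2–96.7) | 45/47 = 95.74% (85.5–99.5) |

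Miscounting as success rather than non-success costs 1 point per subject at N=100 and 2 points at N=50. Against leaving the doses out, the cost for three subjects is 96.00 − 95.88 = 0.12 point and 96.00 − 95.74 = 0.26 point.

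**The case for a change.** The best argument for a change is that a single adjective carries the whole rule. No sentence says that an observed Week 4 dose is a failure, an exclusion or not attempted, and the table shell does not separate by place. The return option is allowed, so such a dose would not clearly be a protocol deviation. One programmer could take the investigator's assessment at face value and another could apply the endpoint wording, and their percentages would differ. A short sentence before database freeze would cost almost nothing.

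Part of this stands. The documents do not state the case expressly, and the handling of an unscheduled on-site record is unclear. Excluding such doses is also defensible in principle, and the choice has some size: with three subjects, 95.88 − 93.00 = 2.88 points at N=100 and 95.74 − 90.00 = 5.74 points at N=50. But SAP 7.2 already states the denominator, so exclusion would depart from the text. The route to a false success also requires an analyst to set aside the wording of the numerator.

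The surrounding plan points the same way. In-clinic dosing and the Observer Checklist are scheduled only at Visits 2 and 4, and the Week 4 checklist table is for at-home injection. The site-contact item in that table asks about contact before the injection for more training, which fits a visit followed by a home dose. LIST_INJ1 has a column for clinic or home injection and shows an unscheduled in-clinic row, so the listing is designed to make any such case visible. Whether the source forms capture place cannot be judged from these documents.

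**Conclusion.** The concern does not hold as a fault in the analysis. The literal numerator and denominator in SAP 7.2 keep an observed clinic dose from counting as a Week 4 success, and they give the same answer an added rule would give. What is left is a missing detail about a narrow case: an on-site, observed, unaided first attempt. A one-line clarification would be harmless, but the plan does not need it.

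The possible effect, if the wording were ignored, is 1 point (N=100) or 2 points (N=50) per subject against counting the dose as not successful. Against exclusion it is at most 0.26 point for up to three subjects. These figures rest on an assumed starting value of 96% and an assumed one to three subjects per label group. The Week 8 primary endpoint is unaffected, and the study is descriptive with no hypothesis test.
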